1.5 Planned sample size

No formal sample size calculation was performed for the study. The sample size of up to 12 patients, including at least 4 patients with VWD type 3, is based on a communication with the FDA and on EU guideline CPMP/BPWG/220/02 calling for a trial in at least eight children with VWD under the age of six years, three of whom should have type 3 VWD. A sample of 12 patients was finally selected to accommodate for drop-outs.

2 GENERAL INFORMATION

2.1 Background details

All study data will be transferred to a SAS database (version 9.4 or later) for statistical analysis purposes. Data will be imported from a Data Capture System via validated SAS programs. The SAP will be finalized before database lock after agreement with the Sponsor on subject disposition and coding.

2.2 Deviations from the trial protocol with impact on statistical analyses

The following general deviations from the protocol will be considered as being important for the statistical analysis:

- Patients who entered the study although they did not satisfy the eligibility criteria.
- Patients who received the wrong treatment or incorrect dose.
- Patients with substantial deviations from the timing foreseen for the prophylactic treatment regimen.
- Patients who received forbidden concomitant medication.

Statistical Analysis Plan	Version 2.0		Page 8 of 27
Sponsor	Octapharma	Protocol No	WIL-33

2.3 Individual protocol deviations

Apart from violations of in- or exclusion criteria the table below lists conditions that may affect the evaluation of subject data and the proposed actions:

Condition	Decision Rule
Subjects not exposed to wilate	Exclude from PP, FAS, SAF
Subjects with substantial deviations from the prophylactic treatment regimen, as agreed during the DRM	Exclude from PP
Subjects without evaluable PK-samples	Exclude from PK
Subjects with major PK over- or underdosing	Exclude from PK-PP

A detailed review of all documented and derived deviations from protocol will be part of a Data Review Meeting (DRM) before database lock. During this DRM the impact of protocol deviations on the analysis will be assessed and the conclusions recorded.

A complete listing of documented and derived protocol deviations and the judgment for assessment of subject disposition will be signed before database lock. A description of protocol violations that led to exclusion from any analysis sets will be included in the table part of the CSR.

3 ANALYSIS POPULATIONS

In general, the disposition of subjects will be displayed for the subject populations defined below.

Membership of subjects will be decided upon in a DRM with the Sponsor before database lock. The proper flags for analysis sets exclusion (e.g., exclusion from PP set), will be included in the analysis datasets. The protocol deviation list should be finalized before database lock.

- The analysis of safety will be based on the SAF set.
- The evaluation of the primary endpoint will be performed on the FAS (ITT analysis) and on the PP set (PP analysis).
- For secondary and exploratory endpoints, ITT and PP analyses will be carried out, unless these analysis sets differ by no more than 1 patient.
- Analysis of the efficacy and safety of *wilate* in surgeries will be based on the SURG set.
- Analysis of the PK properties of *wilate* will be based on the PK set.

3.1 Screening Failures

Subjects who signed the Informed Consent Document but did not receive IMP will be considered screening failures.

Statistical Analysis Plan	Version 2.0		Page 9 of 27
Sponsor	Octapharma	Protocol No	WIL-33

3.2 Safety Analysis Set

The Safety Set (SAF) will include all patients who received at least one dose of IMP.

3.3 Full Analysis Set

The Full Analysis Set (FAS), defined according to the intention-to-treat (ITT) principle, will include all enrolled patients who received at least one dose of IMP after the completion of the PK assessment.

3.4 Surgery Analysis Set

The Surgery Analysis Set (SURG) will be a subset of the FAS, containing all patients who underwent a surgical procedure during their prophylactic treatment phase and were treated with IMP prior to the start of surgery or intraoperatively.

3.5 Pharmacokinetic (PK) Set

The Pharmacokinetic Set will be a subset of the SAF containing all patients for whom a valid PK profile could be obtained from the PK visit. Invalid samples/PK profiles (e.g. hemolyzed samples, incomplete PK) as well as patients with inhibitors at the PK visit will be excluded from the PK-analysis during DRM.

3.6 Pharmacokinetic Per-protocol Set

The Pharmacokinetic Per-Protocol set (PKPP) will be a subset of the PK Set excluding subjects with a major protocol deviation regarding PK dosing.

3.7 Per-protocol Set

The Per-Protocol Set (PP) is a subset of subjects in the FAS.

It includes all subjects who were treated according to the protocol without any important protocol deviations (as finally defined during DRM) and had a valid primary endpoint (valid documentation of BEs during 12 Months (- 4 weeks) of prophylactic treatment).

3.8 Subgroup analyses

As mentioned in section 1.3 of the SAP, an additional multimer analysis using low- and high-resolution electrophoresis gels will be performed only in the subgroup of patients with hereditary type 3 VWD with ≥ 14.5 kg body weight. The multimer composition will be investigated over time for PK sampling time points 15 minutes, and 24 hours after IMP injection (for details see section 4.7.3).

The analysis of demographics and all efficacy analyses (except for the VWF type 3 subgroup) will be stratified by the following subgroups:

- VWD type ('severe type 1', 'type 2' and 'type 3')
- Sex ('Female', 'Male')

The safety analysis will be stratified by sex.

Statistical Analysis Plan	Version 2.0		Page 10 of 27
Sponsor	Octapharma	Protocol No	WIL-33

4 STATISTICAL ANALYSES

All statistical analyses will be performed using the SAS® software (Version 9.4 or later).

Descriptive statistics will be given for the analysis set relevant for the different endpoints. For baseline and basic variables, they will also be given for the safety analysis set.

If not stated otherwise the following standard types of descriptive analyses will be presented:

– Descriptive statistics for continuous data

N, mean, SD, min, lower quartile, median, upper quartile and max will be presented. These descriptive statistics will be determined for measured values and optionally for differences to baseline.

– Descriptive statistics for categorical data

Absolute frequencies (N) will be presented with 0, relative frequencies (%) with at least 1 decimal. Percentage bases (denominators) will be identified in the table title or footnote (i.e. all subjects at risk, all non-missing cases, all cases). For changes from baseline, shift tables will be generated (prophylactic treatment regimen, vital signs, safety laboratory)

– Inferential statistics

Unless otherwise stated, all statistical tests will be performed two-sided and at a type I error probability of $\alpha=0.05$.

Unless otherwise stated, all confidence intervals (CIs) will be derived two-sided and at a confidence probability of $1-\alpha=0.95$.

All p-values will be rounded to 4 decimals ($p<0.0001$ will be displayed if the p-values are less than 0.0001). Unless otherwise specified, statistical significance will be declared if the rounded p-value will be less than 0.05.

– PK/IVR analysis

For presentation of pharmacokinetic concentrations/activities for FVIII and VWF in tables and figures and for PK/IVR analysis, values below the lower limit of quantitation (LLOQ) will be set to $\frac{1}{2}$ LLOQ. In case that more than half of the values per timepoint are below LLOQ descriptive statistics (except maximum) will not be calculated.

For PK analysis plasma concentrations/activities and PK parameters will be summarized using descriptive statistics (number of values (n) or number of subjects (N), geometric mean, geometric coefficient variation (CV%), arithmetic mean, standard deviation (SD), median, minimum and maximum). The geometric mean is calculated as the exponential of the arithmetic mean calculated from data on a log scale. The CV% is calculated as $CV\% = 100 \cdot \sqrt{\exp(s^2) - 1}$ where s is the standard deviation of the data on a log scale.

– Figures

4.1.2 Missing data

In general, missing data will not be imputed. Calculations pertaining to the derivation of the TABR will be based on documented time periods only.

Only in case of missing body weight will the last available body weight measurement be used for calculating the dose per kg body weight (last observation carried forward, LOCF).

Statistical Analysis Plan	Version 2.0		Page 12 of 27
Sponsor	Octapharma	Protocol No	WIL-33

4.1.3 Pooling of centres

All tables will be presented in total over all participating countries and centres. The distribution of number of subjects per country and centre will be presented in the disposition section of the report. No pooling of centres will be performed.

For additional standards and conventions applied in the generation of statistical outputs please refer to section 8.

4.2 Demographic and other background data

4.2.1 Basic description

The disposition of subjects (cf. Section 3) will be tabulated for the entire population. Details on protocol deviations will be listed.

Discontinued subjects will be described by frequency distributions including the reasons and in individual listings.

Demographic data (age, weight, height, BMI, race, ethnic group) will be summarized in tables and presented for the SAF and FAS population. Other baseline or background data, e.g. disease-specific information, will comprise descriptive tables for the SAF and FAS population for the following variables:

- Blood group (from medical records or obtained anytime during the study)
- VWF:Ag, VWF:Ac levels from medical records
- FVIII inhibitor level
- Vital Signs (blood pressure, heart rate, body temperature, and respiratory rate) at screening
- Physical examination (normal/abnormal) at screening
- Haemophilia joint health score (HJHS) at screening

The following background data will only be listed:

- Medical history
- Concomitant Medication

4.2.2 Homogeneity tests

Not applicable

4.3 IMP exposure, compliance

For all IVR and PK Assessments, IMP will be administered at the study site, with compliance under the control of the treating investigator.

Adherence with the treatment regimen will be assessed throughout the study. Any change of the prophylactic dose as determined by the responsible treating investigator during the Baseline Visit will be documented in the patient records and eCRF, including start and end dates of each dose and the reason for dose change.

Statistical Analysis Plan	Version 2.0		Page 13 of 27
Sponsor	Octapharma	Protocol No	WIL-33

Parents should be contacted via telephone every 5–7 weeks between the later quarterly visits. All IMP treatment details will be listed.

4.4 Medical history, physical examination

Data on medical history will be listed. Medical history will be coded according to the Medical Dictionary for Regulatory Activities (MedDRA). Codes will be reviewed by a Medical Expert and approved by the sponsor before data base lock.

4.5 Prior and concomitant medication

Any relevant medication taken at time of screening and all new medications taken by the subject during the study period are defined as ‘Concomitant’. Any changes of medications during the study period will also be recorded.

All details of concomitant medications will be listed including, the route, dose, frequency, start and stop date and indication.

Medications will be coded using the WHO Drug Global thesaurus in the version current at the time of study start. Coding will be performed by the CRO and agreed upon with the sponsor before data base lock. (cf. DMP). For concomitant medications tables will show the frequencies of subjects by WHO Drug Global preferred term.

Prior medication will be listed only.

4.6 Concomitant non-pharmacological measures

Not applicable

4.7 Efficacy

The analysis of the efficacy of prophylactic treatment with IMP will be based on the FAS and the PP set unless these analysis sets differ by not more than one patient. Otherwise, the analysis will be presented only for the FAS.

Primarily, all obtained data on treatment characteristics (IMP dosages, frequencies, total consumption), VWF:Ac and FVIII:C incremental IVR of IMP over time and BEs (duration, frequency, efficacy assessment) will be described using summary statistics.

4.7.2 Secondary endpoints

The secondary endpoints of this study are to determine:

- Baseline PK profile characteristics of VWF:Ac (VWF:RCo) and FVIII:C (OS) based on blood samples taken pre-dose (baseline), 30 minutes, 3, 9, 24, 48 and 72 hours after dosing of 80 IU/kg BW IMP

All PK analyses will be based on the PK set. The following PK parameters will be analysed:

- Area under the curve (AUC) and AUC_{norm} (normalised for the administered dose)
- In vivo half-life (T_{1/2})
- Maximum plasma concentration (C_{max})
- Time to reach maximum plasma concentration (T_{max})
- Mean residence time (MRT)
- Volume of distribution (V_d)
- Clearance (CL)
- Incremental in vivo recovery (IVR)

Statistical Analysis Plan	Version 2.0		Page 15 of 27
Sponsor	Octapharma	Protocol No	WIL-33

Pharmacokinetic parameters will be computed for VWF:Ac and FVIII:C vs time profiles. The one-stage (OS) assay for FVIII, actual IMP potencies, and actual sampling times will be used in the calculations. Pharmacokinetic parameters will be derived by non-compartmental methods. To account for residual VWF:Ac and FVIII:C levels the listed parameters will be based on pre-dose-adjusted concentration vs. time profiles (see section 6.1).

- Incremental in-vivo recovery (IVR) of *wilate* for VWF:Ac (VWF:RCo) and FVIII:C (OS) over time (at baseline and at 1, 2, 3, 6, 9, and 12 months of treatment)
- Efficacy of *wilate* in the treatment of spontaneous and traumatic breakthrough BEs based on the proportion of spontaneous and traumatic BEs successfully treated with IMP as assessed by the use of a 4-point ordinal haemostatic efficacy scale (excellent – good – moderate – none).

To assess the haemostatic efficacy of *wilate* in the treatment of breakthrough BEs during prophylaxis, a frequency distribution of all treated BEs that were successfully treated will be presented overall and by severity, along with an exploratory 95% CI for the proportion of successfully treated BEs.

- Efficacy of *wilate* in surgical prophylaxis

The following surgery-related parameters will be analysed (analysis will only be performed if more than 3 treatment-emergent surgeries were reported. Otherwise, data will be listed only):

- Location, severity (minor or major, for definitions see protocol), and type (planned or emergency) of surgery
- Expected and actual duration of surgical procedure
- Expected average/maximum and actual blood loss
- Pre-, intra-, and/or postoperative IMP administration data (only listed)
- Pre-, intra-, and postoperative VWF:Ac and FVIII plasma levels (only listed)
- Routine safety laboratory
- Presence of wound haematomas
- Vital signs (blood pressure, heart rate, body temperature, and respiratory rate)
- Details on concomitantly administered medications (except standard anaesthetics)
- Blood transfusion requirements
- Brief narrative describing the outcome of the intervention
- Overall efficacy assessment at the end of the postoperative period by the responsible treating investigator. Predefined assessment criteria will be used
- Concomitantly administered products (only listed)

Statistical Analysis Plan	Version 2.0		Page 16 of 27
Sponsor	Octapharma	Protocol No	WIL-33

- Narrative describing the outcome and efficacy of the intervention (only listed)
- Inhibitor testing (within 3–8 weeks after the end of the surgery, this visit may coincide with another study visit with scheduled inhibitor testing)

Primarily, all obtained data on treatment characteristics (IMP dosages, frequencies, total consumption) and BEs (duration, frequency, efficacy assessment) will be described by providing summary statistics and supporting figures where appropriate.

In general, the efficacy of *wilate* in the treatment of bleeding episodes will also be presented by type (spontaneous, traumatic, postoperative, other), sites (nose, oral cavity, knee, ankle, elbow, arm, leg, intestinal and other. In addition, knee, ankle and elbow sites will be summarized as site ‘joint’) and severity (minor, moderate, major, life-threatening).

Surgeries and bleeding episodes treated with commercial *wilate* will not be excluded from efficacy analysis of *wilate* in surgical prophylaxis and efficacy analysis of *wilate* in treatment of bleeding episodes, respectively. However, commercial *wilate* will not be included in the dosing analyses.

4.7.3 Exploratory endpoints

Multimer analysis

The exploratory endpoint of this study, which is solely investigated in the hereditary type 3 VWD patients with ≥ 14.5 kg body weight, is a VWF multimer analysis from the PK samples taken at 15 minutes, and 24 hours after IMP injection, by using multimer analysis using low- and high-resolution electrophoresis gels. In addition, the VWF multimer analysis is performed at baseline in all patients.

The multimeric pattern for each sample will be assessed at an independent laboratory. Gels were run at concentrations of 1.2% (low resolution gel) and 1.6% (medium resolution gel), a normal plasma pool sample served as control

Data from the densitometry readings of the gel will be presented as percentage of the multimer bands relative to the total bands. In the 1.2% gels three groups (bins) of multimer peaks will be analyzed, small multimers (bands 1-5), intermediate multimers (bands 6-10) and large multimers (bands > 10) and a narrative description will be provided in addition. For the 1.6% gels, only the triplets narrative description will be provided in line with the reports of the central laboratory. The frequency distribution of standardized narrative descriptions will be displayed for both, the 1.2% and 1.6% gels.

For the screening samples, descriptive statistics of the three multimer groups/bins will be presented per VWD type and sex and for the corresponding plasma pool values.

In VWD type 3 patients, descriptive statistics of the multimer groups will be analysed in addition by time point (i.e. 15 minutes and 24 hours post infusion) including analysis of changes with time (24 hours vs. 15 minutes) as well as in comparison with a normal plasma pool and frequency distribution of standardized narrative description. All individual multimer data will be additionally listed.

Statistical Analysis Plan	Version 2.0		Page 17 of 27
Sponsor	Octapharma	Protocol No	WIL-33

Annualized bleeding rates for treated bleedings

All of the analysis described for the primary end point including robustness analysis (see section 4.7.1) will be repeated for treated bleeds only.

Prior annualized total bleeding rates (pTABR)

The historical total number of bleeding episodes under On-Demand treatment/6 month and under prophylactic treatment/ ≤ 6 month collected at screening will be used to extrapolate the prior TABR (pTABR_{OD} and pTABR_{PROPH}) if a sufficient amount of data are available. This analysis will be purely descriptive.

4.8 Safety

All safety analyses will be based on the SAF population.

The analysis of safety will be based on the occurrence of AEs, e.g. results of immunogenicity screening, thrombogenicity monitoring for sustained excessive FVIII plasma levels (and an increased risk of thrombotic events), and safety laboratory testing. Analysis of AEs will focus on treatment emergent adverse events (TEAEs).

4.8.1 Adverse events

Adverse events will be coded according to the Medical Dictionary for Regulatory Activities (MedDRA) in the version current at the clinical start of the study. The analysis will focus on the incidences and total numbers of treatment-emergent adverse events (TEAEs), i.e., AEs that started or worsened after the first IMP injection. All TEAEs, related TEAEs (i.e., TEAEs at least possibly related to the IMP), and serious TEAEs will be summarised and tabulated according to MedDRA primary system organ class and preferred term.

Other safety parameters (e.g., changes in physical examination findings, Haemophilia Joint Health Score) will be analysed by summary tables or listings.

It is assumed that for each change in intensity, relationship or seriousness of an AE a new entry of the AE was recorded in the data capture database; hence such cases will be analysed like different phases of the same AE.

Incidence tables, i.e. frequency tables of subjects experiencing at least one occasion of the event while at risk (along with the number of different occurrences of the TEAE), will be presented for the following types of adverse events:

- All TEAE irrespective of the causality assessment
- Related TEAEs ('Probably' or 'Possible')
- TEAEs by worst severity
- Serious TEAEs
- Severe TEAEs
- Thromboembolic events

Multiple counts within a PT or SOC (repeated or different included terms or changes in descriptors) will be counted only once for the calculation of incidences.

Statistical Analysis Plan	Version 2.0		Page 18 of 27
Sponsor	Octapharma	Protocol No	WIL-33

A listing of "special cases" containing subject identification, age, sex, AE descriptors, start and end of treatment will be prepared for the following types of TEAEs:

- Serious adverse events (SAE)
- Severe TEAEs
- Related TEAEs ('Probably' or 'Possible')
- Adverse events which led to death
- Adverse events which led to discontinuation
- Thromboembolic events (TEEs)

Serious non-treatment emergent AEs will be listed separately.

Narratives will not be included in section 14.3.3 but will be provided by medical writing in section 12.3.2 of the CSR. All adverse events (i.e. TEAEs as well as non-treatment emergent events) will be listed in section 16.2 of the CSR. However, only TEAEs will be summarized in the tables.

4.8.2 Vital signs

Vital signs parameters (blood pressure, heart rate, body temperature, and respiratory rate) will be assessed at screening, PK visit, after 1, 2, 3, 6, 9 and 12 months at study completion visits and if applicable during surgery.

Descriptive analyses will be performed for values at visits and changes from baseline.

4.8.3 Laboratory variables

The analysis of the safety parameters (lab values for Haematology) recorded during visits and at surgery will be purely descriptive and presented as summary tables or listings.

Time profiles of the safety laboratory parameters will be analysed by presenting sampling statistics for the values as well as their difference to baseline at each time point. Additionally, frequency tables for values outside the normal ranges will be presented.

Time profiles of the safety laboratory parameters will be analysed by presenting sampling statistics for the values as well as frequency tables for positive findings.

Similarly, time profiles of VWF and FVIII inhibitor testing results will be analysed by presenting sampling statistics for the values as well as frequency tables for number of positive findings, along with 95% Pearson-Clopper CIs.

The thromboembolic risk will be monitored by determination of VWF:Ac during the study and especially postoperatively. Descriptive statistics including changes to pre-infusion will be presented by visit and timepoint (with 95% CI) for visits or by operative day and timepoint for surgeries, respectively.

A by subject list of all abnormal lab values will be displayed. In analyses only scheduled, common time points will be displayed. Results from unscheduled visits will only be used in listings. In such listings the normal ranges as well as an indicator of H/L and CLS will be given.

Statistical Analysis Plan	Version 2.0		Page 19 of 27
Sponsor	Octapharma	Protocol No	WIL-33

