1.3 Benefit-Risk Statement

The following adverse drug reactions (ADRs) are known to occur with other VWF/FVIII preparations and may also occur with the use of *wilate* [7]:

- **Hypersensitivity or allergic reactions** (which may include angioedema, burning, and stinging at the infusion site, chills, flushing, generalised urticaria, headache, hives, hypotension, lethargy, nausea, restlessness, tachycardia, tightness of the chest, tingling, vomiting, wheezing) have been observed upon use of *wilate* and may, in some cases, progress to severe anaphylaxis (including shock) with or without fever. On rare occasions, fever has been observed.
- Patients with VWD, especially type 3 patients, may develop **neutralising antibodies (inhibitors) to VWF and/or FVIII**. If expected VWF:Ac and/or FVIII:C activity plasma levels are not attained or bleeding is not controlled with an appropriate dose, an appropriate assay should be performed to determine whether a VWF inhibitor and/or factor VIII inhibitor is present. In patients with high titres of inhibitor, VWF therapy may not be effective, and other therapeutic options should be considered.
- As for all medicinal products prepared from human blood or plasma, infectious diseases due to **transmission of infective agents** cannot be totally excluded. This also applies to pathogens of hitherto unknown origin. The manufacturing process of *wilate*, which includes two viral inactivation steps with different chemical/physical action principles, represents a high standard for plasma-derived concentrates in terms of pathogen safety. The measures taken are considered effective for enveloped viruses such as human immunodeficiency virus (HIV), hepatitis B virus (HBV) and hepatitis C virus (HCV), and for the non-enveloped hepatitis A virus. The measures taken may be of limited value against non-enveloped viruses such as parvovirus B19.
- **Thrombotic events**. When using a FVIII-containing VWF product, the treating physician should be aware that continued treatment may cause an excessive rise in FVIII:C. Patients receiving FVIII-containing VWF products should be monitored for sustained excessive FVIII:C plasma levels, which may increase the risk of thrombotic events. The risk of occurrence of thrombotic events in patients using FVIII-containing VWF products is

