The dose (and duration) of treatment of BEs will depend on the location and extent of bleeding and on the clinical condition of the patient.

Generally, 1 IU/kg BW VWF:Ac and FVIII:C raises the plasma level by 1.5–2% of normal activity for the respective protein, but this increase may be lower in children below the age of 6 years. Usually, about 20–50 IU/kg BW *wilate* are necessary to achieve adequate haemostasis. This will raise the VWF:Ac and FVIII:C in the patients by approximately 30–100% [12].

Recommendations for the dosing in the treatment of BEs in paediatric patients under 6 years of age has been adapted from the US Package Insert [13] and is shown in **Table 4**.

Table 4 *wilate* Dosage Recommendations for the Treatment of BEs

Dose Type	Minor haemorrhage	Major haemorrhage
Loading dose	30–50 IU/kg BW	50–80 IU/kg BW
Maintenance dose	30–40 IU/kg BW every 12–24 hours	30–50 IU/kg BW every 12–24 hours
Therapeutic goal	Maintain VWF:Ac and FVIII:C trough levels >30%	Maintain VWF:Ac and FVIII:C trough levels >50%

After the initial treatment phase of a BE, any further treatment to avoid re-bleeding is to be documented as “prophylactic treatment to avoid re-bleeding” until the transition to the regular prophylactic treatment schedule.

5.4.4 *wilate* Dose for Surgical Prophylaxis

For prevention of bleeding in case of surgery, VWF:Ac peak levels of 50% should be achieved for minor surgeries and VWF:Ac peak level of 100% should be achieved for major surgeries.

An appropriate dose should be re-administered every 12–24 hours of treatment. The dose and duration of the treatment depend on the clinical status of the patient, the type and severity of bleeding, VWF:Ac and FVIII:C levels.

In patients receiving FVIII-containing VWF products, plasma levels of FVIII:C should be monitored to reveal sustained excessive FVIII:C plasma levels, which may increase the risk of thrombotic events. Accordingly, FVIII activity levels should not exceed 200%.

Recommendations for the dosing in surgical prophylaxis in paediatric patients under 6 years of age has been adapted from the US Package Insert [13] and is shown in **Table 5**.

Table 5 *wilate* Dosage Recommendations for Surgical Prophylaxis

Dose type	Minor surgeries (including tooth extractions)	Major surgeries
Loading dose	40–60 IU/kg BW	60–80 IU/kg BW

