7.4.5 Laboratory Tests

The laboratory parameters shown in **Table 10** will be investigated during the study at the time points specified in **Section 6.1**.

Table 10 Laboratory Sampling Flowchart

Laboratory Assessments	Screening Visit	PK Visits	1-Month IVR Visit	2-Month IVR Visit	3-Month IVR Visit	6-Month IVR Visit	9-Month IVR Visit	Study Completion (12-Month) IVR Visit
LOCAL LAB								
Determination of AB0 blood group, unless derivable from medical history			x [1]					
Routine safety laboratory	x							x [2]
CENTRAL LAB								
VWF:Ac (VWF:RCo)	x	x [3]	x [4]	x [4]	x [4]	x [4]	x [4]	x [4]
FVIII:C (OS)		x [3]	x [4]	x [4]	x [4]	x [4]	x [4]	x [4]
VWF and FVIII inhibitors	x				x [2]	x [2]	x [2]	x [2]
VWF multimer analysis	x	x [5]						
Retention samples for possible virus marker testing	x							

[1] If unknown, can also be shifted to a later timepoint

[2] Before injection

[3] Before injection and at 15 min, 3 hr, 9 hr, 24 hr, 48 hr and 72 hrs after injection

[4] Within 60 min before and 15±5 min after injection

[5] For VWD type 3 patients ≥14.5 kg BW, samples from 15 min and 24 hrs will be used for additional multimer analysis

An effort was made in this study to avoid invasive procedures and repeated blood sampling in paediatric patients, in agreement with EU guidelines. The *Ethical Considerations for Clinical Trials on Medicinal Products conducted with the Paediatric Population* will be followed during the conduct of WIL-33.

For sampling, the Committee recommends that per individual, trial-related blood loss should not exceed 3% of the total blood volume during a period of four weeks and should not exceed 1% at any single time. The total volume of blood is estimated at 90 ml/kg BW; in mean 3% is around 2.7 mL blood per kg BW [19].

Blood Sampling

The *actual* date and time of any blood sampling must be recorded in the eCRF, on the label of the laboratory tubes and on the corresponding laboratory shipment forms. The exact sampling volumes needed, and further specific processes will be described in the laboratory manual.

EDTA Blood

Around 2 mL (or less, as required by the local laboratory) of EDTA blood will be collected for the measurement of haematology parameters (RBC count, WBC count, haemoglobin, haematocrit, platelet count) at the screening and at completion visit. All haematology tests are to be done at the local laboratory in accordance with local requirements.

Citrated Plasma

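### SAP 4.8.3 uses VWF:Ac as the laboratory marker of thromboembolic risk, whereas SAP 4.8 and the protocol name sustained excessive FVIII:C, and no safety summary of FVIII:C is specified

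*SAP*

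**What the plan says.** SAP 4.8.3 (Laboratory variables) names the marker: "The thromboembolic risk will be monitored by determination of VWF:Ac during the study and especially postoperatively". The output follows directly: "Descriptive statistics including changes to pre-infusion will be presented by visit and timepoint (with 95% CI) for visits", with a corresponding summary by operative day and time point for surgeries. The passage mentions neither FVIII:C nor any threshold.

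The parent section, SAP 4.8, describes something else: "thrombogenicity monitoring for sustained excessive FVIII plasma levels (and an increased risk of thrombotic events"). Protocol 9.2.3 (Safety Analysis Plan) says the same. Protocol 1.3 (Benefit-Risk Statement) gives the reason: "Patients receiving FVIII-containing VWF products should be monitored for sustained excessive FVIII:C plasma levels, which may increase the risk of thrombotic events". Protocol 5.4.4, on surgical dosing, adds a level: "Accordingly, FVIII activity levels should not exceed 200" per cent.

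FVIII:C is collected alongside VWF:Ac. In protocol Table 10 both are sampled throughout the PK visit and, at each IVR visit, "Within 60 min before and 15±5 min after injection". For surgeries, SAP 4.7.2 plans "Pre-, intra-, and postoperative VWF:Ac and FVIII plasma levels (only listed").

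**The concern.** The SAP's general safety statement and its specified table name different analytes. A programmer builds from the section that defines the output, and here that section is 4.8.3. The resulting table would describe VWF:Ac and leave unanswered the question that SAP 4.8 and the protocol pose about FVIII:C.

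This matters because thrombogenic potential is a stated secondary objective and the trial is small. If no child has a thromboembolic event, the two-sided 95% Clopper-Pearson upper limit is 1 − 0.025^(1/12) = 26.5% with 12 children and 1 − 0.025^(1/8) = 36.9% with 8. An empty event table would therefore say little, and the laboratory marker is a useful second source of evidence.

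**Working it through.** **Which analyte each section names**

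- Protocol 1.3: FVIII:C, as an excessive rise under continued treatment.
- Protocol 5.4.4: FVIII:C, with the 200% level, in the surgical section only.
- Protocol 9.2.3: FVIII.
- SAP 4.8: FVIII.
- SAP 4.8.3: VWF:Ac.

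No other section makes VWF:Ac the thrombotic marker. The change log for SAP version 2.0 does not mention a change of marker.

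**Whether other planned FVIII:C outputs fill the gap**

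- PK parameters are computed after subtracting the pre-dose level (SAP 6.1: Cn(adj) = Cn − C0), and IVR = (Cmax − C0) × BW / D. Both remove the residual level, which is where accumulation would show.
- SAP section 4 summarises PK activities, including the maximum. The PK profile, however, follows one dose after a washout of at least 72 hours, so it cannot show a rise under continued treatment.
- PK outputs use the PK set, which drops invalid profiles and patients with inhibitors at the PK visit. SAP 4.8 requires the safety set for safety analyses.
- Perioperative levels are listed only (SAP 4.7.2). This also conflicts with the operative-day statistics in 4.8.3.
- SAP 4.8.3 describes its safety parameters as haematology values, and protocol 7.4.5.2 does not count FVIII:C among those. Whether the listing of abnormal values covers FVIII:C is unclear.

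**Data available per child.** The PK visit gives 7 FVIII:C samples (pre-dose, 15 minutes, 3, 9, 24, 48 and 72 hours). The six IVR visits give 6 × 2 = 12. That is 19 scheduled values, of which 1 + 6 = 7 are pre-infusion.

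**Whether VWF:Ac could stand in for FVIII:C.** The inputs are:

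- a rise of 1.5–2% per IU/kg for both proteins (protocol 5.4.3);
- a 1:1 product ratio (protocol 5.1);
- VWF:RCo below 20% for eligibility, with no FVIII:C criterion (protocol 4.1);
- a PK dose of 80 IU/kg, with 70–85 acceptable (protocol 5.4.1);
- prophylaxis at 30–50 IU/kg (protocol 5.4.2).

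The protocol's own figure reproduces: 20 × 1.5 = 30% and 50 × 2 = 100%, matching its 30–100% for 20–50 IU/kg.

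The peak is the pre-dose level plus dose × (1.5 to 2). The VWF:Ac ceiling is 20 + 2 × dose. FVIII:C passes 200% if its pre-dose level exceeds 200 − dose × (1.5 to 2).

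| Dose (IU/kg) | Rise (%) | VWF:Ac peak from below 20% | Pre-dose FVIII:C needed to pass 200% (at 1.5 / at 2) |
|---|---|---|---|
| 30 | 45–60 | below 80% | above 155% / 140% |
| 50 | 75–100 | below 120% | above 125% / 100% |
| 80 | 120–160 | below 180% | above 80% / 40% |
| 85 | 127.5–170 | below 190% | above 72.5% / 30% |

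The 1:1 ratio equalises the dose of the two proteins but not their starting levels, so VWF:Ac is not a guaranteed proxy. The table is conditional only. The documents give no pre-dose FVIII:C, protocol 1.2 and 5.4.3 say recovery may be lower under age 6, and a single peak does not show sustained elevation.

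**The case against.** The strongest reply is that little is lost. The protocol's endpoint for thrombogenicity is the incidence of clinical events, and SAP 4.8.1 tabulates and lists these. FVIII:C is summarised under PK, used for recovery through month 12 and listed around surgery, and in 8–12 children a listing can reveal an exceedance. SAP 4.8 itself commits to FVIII monitoring. The full list of tables is a separate document, so an FVIII:C safety table may exist there. The study is descriptive and the primary endpoint is untouched.

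Most of this stands, and it limits the point. A reader might infer that the trial would miss a thrombogenic signal. The documents do not support that, because events and FVIII:C values are both reported elsewhere.

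A reader might also infer that children are expected to pass 200% FVIII:C unseen. That needs an assumed baseline, and at prophylactic doses of up to 50 IU/kg the pre-dose level would have to exceed 100–125%. Nor is 200% stated as a study-wide limit, since it appears only in the surgical section. Finally, 180% is not a firm ceiling for VWF:Ac. The permitted PK dose of 85 IU/kg gives 190%, and a pre-dose level below 20% is not assured during ongoing prophylaxis.

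The reply does not remove the contradiction between SAP 4.8.3 and SAP 4.8, and it does not supply a specified safety summary of absolute FVIII:C.

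**Conclusion.** The contradiction is real, both within the SAP and against the protocol. As written, the only specified thrombogenicity laboratory table summarises an analyte that no other section links to the risk. The consequence is confined to that table: no data are lost and event reporting is unaffected. The SAP text specifies no safety-set summary of absolute FVIII:C during prophylaxis, no definition of sustained excess and no count above 200%.

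This is a should-fix point. The conclusion rests on comparing the sections and does not depend on the peak-level arithmetic, which shows only that the two analytes can diverge under stated assumptions. The separate list of tables was not available to check.

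**What to change.** Reconcile SAP 4.8.3 with SAP 4.8 and protocol 9.2.3, as follows.

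- Make FVIII:C (one-stage) the thrombogenicity marker in 4.8.3. Summarise absolute pre- and post-infusion values on the safety set by visit and time point, and by operative day where sampled.
- Show change from the baseline pre-dose level. Change from the same visit's pre-infusion value would cancel any accumulation.
- Define sustained excess for analysis before database lock, for example from repeated pre-infusion values.
- Report descriptively the number of children with any FVIII:C above 200%, and list them. Note that the protocol states this level in its surgical section. A mean with a 95% CI in about 12 children can hide one child.
- Keep VWF:Ac as a supportive summary.
- Align the listing-only rule for perioperative levels in SAP 4.7.2 with the operative-day statistics in 4.8.3.

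The cost is SAP wording and one extra table. No new samples are needed, because FVIII:C is already taken at every PK and IVR time point.
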